5.5 Standard of Care Migraine Medications

Use of standard of care migraine medication during the Screening Phase and through the Follow-up Week 8 Visit will be recorded by the subject on the concomitant medication paper diary and reported to the site. Migraine medications include both prophylactic and acute migraine medications.

5.5.1 *Prophylactic Migraine Medications*

Subjects may not use more than 1 of the following medications with possible migraine-prophylactic effects, regardless of indication, if not otherwise prohibited by the protocol. Doses must be stable **within 3 months (12 weeks) prior to the Screening Visit** and throughout the study. Use of more than 1 of the following medications is prohibited within 3 months (12 weeks) prior to the Screening Visit and throughout the study.

Prophylactic migraine medications that are permitted during the study include:

- Topiramate, gabapentin
- Beta blockers (such as: atenolol, bisoprolol, metoprolol, nadolol, nebivolol, pindolol, propranolol, timolol)

- Tricyclic antidepressants (such as: amitriptyline, nortriptyline, protriptyline)
- Venlafaxine, desvenlafaxine, duloxetine, milnacipran
- Flunarizine, lomerizine
- Lisinopril, candesartan
- Clonidine, guanfacine
- Cyproheptadine
- Methysergide
- Pizotifen
- Feverfew, magnesium (≥ 600 mg/day), riboflavin (≥ 100 mg/day)
- Botox®

The above listed medications are the only prophylactic migraine medications allowed.

5.5.2 Acute Migraine Medications

Subjects may use their permitted standard of care medication if needed for acute treatment of a migraine throughout the study.

Acute migraine medications that are permitted during the study include the following:

- triptans,
- aspirin,
- ibuprofen,
- baclofen,
- acetaminophen up to 1000 mg/day for a maximum of 2 consecutive days at a time (this includes Excedrin Migraine),
- Naprosyn (or any other type of non-steroidal anti-inflammatory (NSAID)),
- antiemetics (e.g., metoclopramide or promethazine),
- muscle relaxants for rescue during the study.

The above listed medications are the only acute migraine medications allowed.

If a subject takes a tablet of study drug and experiences a migraine later that day, after dosing with study drug for the day, then the subject may take their **permitted acute migraine medication** as described in this section of the protocol. **During the Open-label Treatment Phase, subjects are not allowed to take more than 1 tablet of study drug daily.**

5.6 Contraception

The investigator or their designee, in consultation with the subject, will confirm that the subject is utilizing an appropriate method of contraception for the individual subject from the permitted list of contraception methods (see [Section 16.5.4](#)) and will confirm that the subject has been instructed in its consistent and correct use.

The investigator or designee will inform the subject of the need to use acceptable effective contraception consistently and correctly and document the conversation and the subject's affirmation in the subject's chart. Subjects need to affirm their consistent and correct use of at least 1 of the selected methods of contraception, considering that their risk for pregnancy may have changed since the last visit.

The investigator or designee will inform the subject of the need to use acceptable effective contraception consistently and correctly and document the conversation and the subject's affirmation in the subject's chart. Subjects need to affirm their consistent and correct use of at least 1 of the selected methods of contraception, considering that their risk for pregnancy may have changed since the last visit.

5.7 Other Restrictions and Precautions (if applicable)

Not Applicable

5.8 Deviation from Inclusion/Exclusion Criteria and Study Procedures

Any significant event that does not comply with the inclusion / exclusion criteria, study conduct, or study procedures will be documented as a deviation. Deviations will be documented and reported through the clinical monitoring of the study. Deviations will be reported to the IRB/IEC at the frequency required by your IRB/IEC. Prospective approval of protocol deviations to recruitment and enrollment criteria, also known as protocol waivers or exemptions, is not permitted.

6 STUDY CONDUCT AND DESCRIPTION OF STUDY PROCEDURES

6.1 Study Materials

The following study materials will be provided at the study start:

- Investigator File/Regulatory Binder
- Pharmacy Binder
- Drug Accountability Logs
- Sample source documents, where applicable
- Concomitant medication paper diary (take home for subject)
- Investigator Brochure (IB)
- Interactive Web-based Response System (IWRS)
- Electronic Case Report Form (eCRF) instructions
 - Electronic Case Report Forms (eCRFs) will be prepared for all data collection fields
 - All sites will use an Electronic Data Capture (EDC) tool to submit study data to the CRO. Electronic Case Report Forms (eCRFs) will be prepared for all data collection fields including Serious Adverse Events (SAE) Reporting. SAE data (including queries) will be submitted to the CRO using eCRFs.
- Laboratory Kits and Laboratory Manual
 - Safety laboratory, plasma, and serum instructions for all specimens collected will be provided by a designated central laboratory.
- ECG Machine and Instructions
 - ECG equipment, supplies, instructions, and training materials will be supplied by a centralized ECG vendor.
- Back-up forms for CT SAE report, Exposure During Pregnancy and Pregnant Partner Release of Information
- Columbia-Suicide Severity Rating Scale (C-SSRS) forms

- Study system access:
 - Electronic Data Capture (EDC) tool to submit study data to Sponsor / CRO
 - IWRS
 - Central Laboratory vendor portal
 - Central ECG vendor portal

6.2 Safety Assessments

6.2.1 *Vital Signs and Physical Measurements (Height and Weight)*

Vital signs, body weight and height will be recorded at the scheduled visits as outlined in [Table 1](#).

6.2.2 *Electrocardiogram (ECG)*

A standard 12-lead ECG will be recorded during the Screening Phase and at all scheduled visits as outlined in [Table 1](#). A central ECG service will be utilized for reading all ECGs. The over read from the central ECG vendor should be used to determine eligibility for the study. The investigator will determine if any ECG abnormalities are clinically significant or not (see [Section 16.4 Appendix 4](#)).

6.2.3 *Physical Exam*

Subjects will undergo a routine physical examination during the Screening Phase and brief and symptom-directed physical exam at all scheduled visits as outlined [Table 1](#). Physical examinations to include at minimum examination of heart, abdomen, and lungs, and neurologic system with review of any other system to be guided by symptoms.

6.2.4 *Laboratory Assessments*

The investigator must review the laboratory report, document this review, and record any clinically relevant changes occurring during the study in the AE section of the CRF. The laboratory reports must be filed with the source documents. Clinically significant abnormal laboratory test findings are those which are not associated with the underlying disease, unless judged by the investigator to be more severe than expected for the subject's condition.

6.2.4.1 Safety Laboratory Testing

Blood and urine samples will be obtained as outlined in [Table 1](#) for clinical laboratory evaluations. A central laboratory vendor will be utilized for this study and a laboratory manual will be provided to each site. **If possible, subjects should be fasting for a minimum of 8 hours before laboratory tests.** However, if a subject is not fasting at a given visit, the blood draw should still be performed, and the non-fasting status should be documented.

1. Clinical safety labs:

Hematology: Hemoglobin, hematocrit, red blood cell count, white blood cell count with differential, and platelets

Chemistry: Sodium, potassium, chloride, bicarbonate, calcium; glucose, HbA1c (only collecting at screening, repeat, or UNS), BUN (urea), serum creatinine, uric acid, LDH, total protein, albumin, CK

eGFR using the estimated MDRD formula (calculated at central lab)

2. **LFTs:** AST, ALT, Alkaline Phosphatase and Bilirubin (Total, Direct, Indirect). Additional tests may be obtained to evaluate laboratory abnormalities and/or adverse events; please refer to the Laboratory manual.
3. **Lipid Panel:** Cholesterol, LDL, HDL, triglycerides
4. **Urinalysis:** pH, specific gravity, ketones, nitrites, urobilinogen, leukocyte esterase, protein, glucose, and blood. If blood, protein, or leukocytes are positive, reflex to microscopic examination.
5. **Urine Drug Screen:** For drugs of abuse
6. **FSH:** At screening in female subjects to confirm postmenopausal status, if applicable.
7. **Reflex/add-on tests:**

If ALT or AST $\geq 3 \times$ ULN *OR* total bilirubin $\geq 2 \times$ ULN at any visit after the Baseline Visit, additional reflex or add-on tests may be performed that may include: CK, GGT, and anti-viral serologies. Subjects may have to return to the study site to provide additional blood samples for these laboratory tests. See section on potential Drug Induced Liver Injury ([Section 8.4](#)).

Additional tests may be obtained to evaluate laboratory abnormalities and/or adverse events; please refer to the Laboratory Manual.

6.2.4.2 *Pregnancy Testing*

WOCBP will complete pregnancy tests (serum and/or urine) at specified study visits, prior to taking study drug, and as outlined in [Table 1](#).

6.2.5 *Columbia-Suicide Severity Rating Scale (C-SSRS)*

The Columbia-Suicide Severity Rating Scale (C-SSRS) is a questionnaire used for suicide Assessment.⁹ The C-SSRS “Screening version” will be used at the Screening Visit and the “Since Last Visit version”¹⁰ will be used at subsequent visits in this study.

The C-SSRS Assessment is intended to help establish a person’s immediate risk of suicide. The C-SSRS is a clinician administered scale that should be administered by a certified rater. This scale will be collected on site with a paper form. The C-SSRS should be reviewed by the Investigator or designee before the subject is allowed to leave clinic.

At the Screening Visit, the recall period for completing is 12 months for suicidal ideation and 10 years for suicidal behavior; at all other visits, the recall period for completing the C-SSRS is since the last visit (Table 1).

Any “Yes” responses must be immediately evaluated by the investigator. If the Investigator determines that a subject is at risk of suicide, self-harm, appropriate measures to ensure the subject’s safety and obtain mental health evaluation must be implemented. In such circumstances, the subject must immediately be discontinued from the study. The event should be recorded as either an AE or SAE as determined by the Investigator and reported within 24 hours to the Sponsor.

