- e) Subjects who meet criteria for C-SSRS Suicidal Ideation Items 4 or 5 within the last 12 months prior to screening, OR subjects who endorse any of the 5 C-SSRS Suicidal Behavior Items (actual attempt, interrupted attempt, aborted attempt, preparatory acts, or behavior) within the last 10 years prior to the Screening Visit, OR subjects who, in the opinion of the investigator, present a serious risk of suicide (See [Section 6.2.5](#)).
- f) Previous enrollment in any multiple dose BHV3000 (rimegepant) study, such as BHV3000-201, BHV3000-305, or BHV3000-404 regardless of the number of doses taken. Subjects may be considered for BHV3000-405 (C4951011) if the subject participated in any of the following single dose studies: BHV3000-301, BHV3000-302, BHV3000-303. Note that subjects who were considered screen failures in a past BHV3000 study may be considered after discussion with the Sponsor and written approval is received.
- g) Subjects are excluded if they have had no therapeutic response with $>$ 2 of the 8 medication categories for prophylactic treatment of migraine listed in [Appendix 3](#) after an adequate therapeutic trial. Additional details can be found in [Section 16.3 Appendix 3](#).
- h) Participation in any other investigational clinical study while participating in this clinical study. Participation in a COVID-19 mRNA vaccine study (vaccine must be authorized

under FDA emergency use authorization or approval) who are at least 30 days post last dose of the vaccine are permitted to be screened for this study.

- i) Past participation in a clinical study within 30 days prior to the Screening Visit. Note: Individuals who do not meet the criteria for participation in this study (screen failure) may be considered for re-screening in select circumstances (e.g., previously pregnant, screening window too long, ineligibility was due to 1 of the eligibility criteria that may have changed due to medical intervention or 1 of the eligibility criteria modified in a protocol amendment). In all possible re-screening circumstances, the situation must be discussed with the Sponsor prior to re-screening, with approval in writing from the Sponsor prior to re-screening.
- j) Please see [Section 5.4](#) for prohibited medications and [Section 5.5.2](#) for permitted acute migraine medications.

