3.2.3 Exploratory Objective Estimands

The estimands corresponding to the exploratory objectives are shown in Table 2.

Table 2 Exploratory Objective Estimands

Objective	Frequency of AEs potentially associated with drug abuse during the OLT Phase
Safety Endpoint	Number and percentage of subjects with potential drug abuse AEs on treatment
Summary	Frequency for the safety analysis set
Intercurrent Events	Study drug discontinuation: while-on-treatment strategy
Objective	Frequency and intensity of hepatic-related AEs during the OLT Phase
Safety Endpoint	Number and percentage of subjects with hepatic-related AEs by intensity on treatment
Summary	Frequency for the safety analysis set
Intercurrent Events	Study drug discontinuation: while-on-treatment strategy
Objective	Frequency of LFT elevations based on fold changes above ULN during the OLT Phase
Safety Endpoint	Number and percentage of subjects with LFT elevations (ALT, AST, ALP, or TBL) based on fold changes above ULN on treatment
Summary	Frequency for the safety analysis set with LFT data on treatment
Intercurrent Events	Study drug discontinuation: while-on-treatment strategy
Objective	Frequency of ALT or AST > 3x ULN concurrent with TBL > 2x ULN during the OLT Phase
Safety Endpoint	Number and percentage of subjects with ALT or AST > 3x ULN concurrent with TBL > 2x ULN on treatment
Summary	Frequency for the safety analysis set with LFT data on treatment
Intercurrent Events	Study drug discontinuation: while-on-treatment strategy

Objective	Frequency of ALT or AST > 3x ULN in temporal association with nausea, vomiting, anorexia, abdominal pain, or fatigue during the OLT Phase
Safety Endpoint	Number and percentage of subjects with ALT or AST > 3x ULN concurrent with AEs of nausea, vomiting, anorexia, abdominal pain, or fatigue on treatment
Summary	Frequency for the safety analysis set with LFT data on treatment
Intercurrent Events	Study drug discontinuation: while-on-treatment strategy
Objective	C-SSRS during the OLT Phase
Safety Endpoint	Number and percentage of subjects with any of the following findings on treatment: suicidal ideation; suicidal behavior; suicidal ideation or behavior; and non-suicidal self-injurious behavior.
Summary	Frequency for the safety analysis set with C-SSRS data on treatment
Intercurrent Events	Study drug discontinuation: while-on-treatment strategy

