6.4.5 C-SSRS

The C-SSRS is a clinician administered questionnaire used to help establish immediate risk of suicide. The C-SSRS is administered at all visits except Follow-Up Week 8. At the Screening Visit, the recall period for completing is 12 months for suicidal ideation and 10 years for suicidal behavior; at all other visits, the recall period for completing the C-SSRS is since the last visit.

Frequency tables of C-SSRS suicidality are provided for the following analysis periods and analysis sets:

- On-treatment for the safety analysis set (supports exploratory objective #6)
- Follow-up for the follow-up safety analysis set.

Refer to the Core SAP for calculation of C-SSRS parameters and TLF contents.

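### The planned C-SSRS tables cannot separate new or worsened suicidality from ideation present before dosing that persists or recurs on treatment

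*Protocol*

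**What the plan says.** **Collection.** SAP 6.4.5 states: "The C-SSRS is administered at all visits except Follow-Up Week 8". Protocol Table 1 agrees, so each treated subject should have two C-SSRS forms, Screening and Baseline, from before dosing or the day it starts. Protocol 6.2.5 gives the recall periods in one sentence. The first half reads "At the Screening Visit, the recall period for completing is 12 months for suicidal ideation and 10 years for suicidal behavior", and the second half reads "at all other visits, the recall period for completing the C-SSRS is since the last visit".

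**Entry.** Protocol 5.3, criterion 7e, excludes three groups:
- "Subjects who meet criteria for C-SSRS Suicidal Ideation Items 4 or 5 within the last 12 months prior to screening"
- "subjects who endorse any of the 5 C-SSRS Suicidal Behavior Items" within 10 years before Screening
- those who, "in the opinion of the investigator, present a serious risk of suicide"

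Ideation items 1 to 3 and non-suicidal self-injury are not on this list.

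**Endpoint.** For exploratory objective 6, SAP Table 2 counts subjects with any of these on treatment: "suicidal ideation; suicidal behavior; suicidal ideation or behavior; and non-suicidal self-injurious behavior". It sets no condition that the finding be new or worse than before dosing.

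**Outputs.** SAP 6.4.5 says "Frequency tables of C-SSRS suicidality are provided for the following analysis periods and analysis sets", and the list has two entries: on-treatment for the safety set and follow-up for the follow-up safety set. The calculation of C-SSRS parameters and the table contents are left to the Core SAP.

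**The concern.** The study has a single arm, so a subject's own status before dosing is the only internal reference for an on-treatment finding. The plan collects that reference, but this SAP does not use it for objective 6. A subject with passive ideation at Screening and Baseline who still reports it at Week 2 adds one to the on-treatment count. So does a subject whose ideation first appears at Week 2.

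The resulting percentage could be misread in two ways. It could look like a drug effect when part of it is what subjects brought into the trial. It could also hide real worsening, because a subject who moves from a low to a higher ideation level adds one in the same way as a subject who has not changed. Both matter in a post-marketing required study whose purpose is to describe safety under more frequent dosing.

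**Working it through.** No figure in the plan is at stake, so the main check sets the rules side by side.

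**1. Who can enter with a finding.** Exclusion 7e and the Screening form use the same windows (12 months for ideation, 10 years for behavior). In subjects who meet the criteria, Screening should show no item 4 or 5 ideation and no suicidal behavior. The gap is therefore confined to ideation items 1 to 3 and non-suicidal self-injury. Exclusions 2c and 2m narrow this group further. They remove, among others, subjects with a major depressive episode in the last 12 months and those with bipolar disorder. Subjects with depression or anxiety on one stable daily medication per disorder, and no such episode, are not removed by 2c.

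**2. What an on-treatment answer covers.** The Week 2 form looks back to Baseline, and each later form to the visit before it. SAP 7.2 and Table 3 place Screening and Baseline in a separate pretreatment period. A finding must therefore be present after the previous visit to count. Two small leaks remain. Dosing may start the day after Baseline, and if the Baseline form is missing, the Week 2 recall reaches back to Screening, 3 to 14 days before Baseline.

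**3. How the endpoint classes typical courses** (hypothetical subjects; highest ideation item reported):

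| Screening | Baseline | On treatment | Counted in Table 2? | New or worse than Baseline? | New or worse than Screening? |
|---|---|---|---|---|---|
| 1 | 1 | 1 | Yes | No | No |
| None | None | 1 | Yes | Yes | Yes |
| 1 | 1 | 3 | Yes | Yes | Yes |
| 3 | None | 3 | Yes | Yes | No |
| 3 | None | None | No | No | No |

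Each counted subject adds 1/285 = 0.35%. The four counted courses cannot be told apart in a count of any ideation. The fourth row also shows that the choice of pretreatment reference matters.

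**4. What else in this SAP uses pretreatment C-SSRS.** The only stated use is the eligibility deviation in SAP 9.1, which covers items 4 and 5 and suicidal behavior. Pretreatment items 1 to 3 and self-injury have no named output. The SAP revision history (Version 3) records that the by-subject C-SSRS listing was taken out. By contrast, SAP 6.4.2.1 and 6.4.2.2 name shift tables for graded laboratory tests and LFTs. SAP 6.4.2.3, 6.4.3.1 and 6.4.4.1 name changes from baseline for laboratory tests, vital signs and ECG.

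**5. Possible size (assumption only).** The documents give neither the share q of subjects who enter with such findings nor the share r of those who report them again on treatment. With n = 285, the expected number is n × q × r, and the chance of at least one is 1 − (1 − q × r)^285, treating subjects as independent:

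| q | r | Expected subjects | Percent of 285 | Chance of at least one |
|---|---|---|---|---|
| 1% | 10% | 285 × 0.01 × 0.10 = 0.3 | 0.1% | 25% |
| 3% | 30% | 285 × 0.03 × 0.30 = 2.6 | 0.9% | 92% |
| 5% | 50% | 285 × 0.05 × 0.50 = 7.1 | 2.5% | >99% |

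The actual denominator is the safety set with on-treatment C-SSRS data, which may be below 285.

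**The case against.** A reader who stops at the Screening recall might infer that 12 months of ideation or 10 years of behavior is reported as an on-treatment finding. The documents do not support that. The second half of the same sentence limits later forms to the time since the last visit, and pretreatment answers have their own analysis period. This part of the objection stands in full. What remains is ideation or self-injury that persists or recurs after dosing starts.

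A reader might also infer that no comparison with pretreatment exists anywhere. That cannot be said. The Core SAP governs C-SSRS parameters and table contents, the templates are in a separate mock document, and neither was supplied. The point is limited to what this SAP states. Even so, SAP 6.4.2 also defers to the Core SAP for table contents, and its subsections still name their shift tables. SAP 8 commits the final report to the outputs described in this SAP.

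Third, important new events have another route. Protocol 8 defines an adverse event as new or worsened. Protocol 6.2.5 requires the investigator to evaluate any positive answer and to record an event when the subject is judged at risk. The SAP plans a suicidality AE table (6.4.1.3) and identifies subjects for narratives (6.4.6). This is real but partial cover: a low-level positive answer not judged to be a risk may never become an AE, yet it enters the C-SSRS percentage.

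Finally, objective 6 is exploratory and worded broadly, and an on-treatment count fits the while-on-treatment estimand. That limits the weight of the point but does not make the count easier to interpret.

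**Conclusion.** The point holds in a limited form. As far as this SAP states, the output for objective 6 will not separate new or worsened suicidality from ideation or self-injury that was present before dosing and persists or recurs. The primary endpoint is not affected.

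The size is unknown. The illustrative 0.3 to 7.1 subjects rests wholly on assumed shares and shows only that a few subjects could make up much of a small percentage. A reader might set such a percentage against the rate of 1 per 100 in the sample-size sections (Protocol 9.1, SAP 5). That comparison is not valid: the figure is an upper confidence bound for an event never observed, not a threshold for C-SSRS findings.

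The conclusion assumes that no Core SAP rule already compares with pretreatment. If one does, what remains is a missing reference in 6.4.5. The change is worth making because it costs little, but it is a moderate improvement to an exploratory analysis.

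**What to change.** First check the Core SAP. If it defines C-SSRS findings relative to pretreatment, or shows pretreatment status in the suicidality tables, cite that rule in SAP 6.4.5 and Table 2.

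If not, keep the crude on-treatment percentage and add the following to SAP 6.4.5 for the safety set:
- **Shift table.** Worst pretreatment ideation level (none, then items 1 to 5 individually) and suicidal behavior (yes/no) against the worst on-treatment level. Pooling items 1 to 3 would hide worsening from 1 to 3.
- **Two references.** Show the Screening responses (12-month and 10-year recall) and the Baseline responses (since last visit) separately. A single worst pretreatment value could mask ideation that had resolved by Baseline and re-emerged on treatment.
- **New or worsened findings.** Report their number and percentage next to the crude percentage, stating which reference is used.
- **Non-suicidal self-injury.** Give it its own yes/no shift where it was recorded before dosing. It has no rank on the ideation scale, and the documents do not say whether the Screening version records it.

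The cost is SAP wording and one extra exploratory table, mainly from forms already collected. No assessment is added. Most cells will probably hold few subjects, so the table should be read descriptively.
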